 - b. Persistence Hypothesis: DCS improvement of delusions compared to placebo will persist at 3 and 6 month follow-up as defined as maintenance of a 20% or greater reduction in the PSYRATS Delusions Subscale total score from baseline.

Tertiary

3. Identify mediators of delusional response to DCS.
 - a. Memory Consolidation Hypothesis: Change in 7-day thematic recall on the Logical Memory Test after the first dose of DCS will predict improvement on the PSYRATS Delusions Subscale total score at 12 weeks.
 - b. Cognitive Flexibility Hypothesis: Change in the number of alternative beliefs generated during the first compared to the second administration of the Alternative Beliefs exercise in the DCS group will predict improvement of the PSYRATS Delusions Subscale total score at 12 weeks.
4. Identify neural differences in patients compared to age-matched healthy control population.
 - a. Network connectivity hypothesis: Decreased connectivity between the hippocampus and prefrontal cortex in patients at rest and during encoding of stories

Study #:S12-02991

and images, DCS enhancement of connectivity.

b. Memory Hypothesis: Patient impairment of network connectivity will predict performance on immediate and 1-week delay memory relative to healthy controls

Background Significance:

Public Health Significance: Delusions remain a serious public health problem, with persistent antipsychotic-resistant delusions present in approximately 30% of schizophrenia patients. In addition, most patients experience intermittent psychotic relapse associated with major disruptions in rehabilitation and recovery. Persecutory delusions are associated with great psychological distress to patients and family members, whereas other forms of delusions commonly result in social and vocational disability, incarceration, and can result in harm to self or others.

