The Psychotic Symptom Rating Scale (PSYRATS) (46): The PSYRATS is a well-validated 17 item, 5 point likert scale which contains 6 items that characterize delusions according to 1.) Amount and duration of preoccupation, 2.) Conviction, 3.) Amount and intensity of distress, and 4.) Disruption to life. We selected the PSYRATS because it frequently has been used in CBT studies, because we previously demonstrated that it captured response to DCS augmentation of CBT, and, unlike the Positive and Negative Syndrome Scale (PANSS), Scale for Assessment of Psychotic Symptoms (SAPS) and the Brief Psychiatric Rating Scale (BPRS), it rates subjective distress and the degree to which delusions disrupt life, both of which are important targets of CBT. Factor analysis has revealed three dimensions (47): preoccupation, conviction and distress/life disruption, with modest correlation between preoccupation and conviction ($r=0.28$) (46). We will use the Delusion Subscale total score as our primary outcome measure and, as an exploratory analysis, we will look at the three domains to further characterize DCS effects.

Assessment of memory consolidation: The Logical Memory Test of the Wechsler Memory Scale (WMS-III) will be used to measure memory consolidation, as in our pilot trial (30). Subjects will be administered Story A one week prior to baseline and will be tested on immediate item and thematic recall. One week later, at baseline they will be tested on 7-day delayed thematic recall. At week 3, one hour after administration of study drug, (immediately before the CBT session), participants will be administered story B, which will be tested for delayed thematic recall immediately prior to administration of study drug the following week. This will allow us to assess the effect of the first dose of DCS on memory consolidation following the same protocol that we used successfully in a previous study (30). The 2-week gap between administration of story A and story B will minimize potential interference between tests.

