Healthy subjects will be consented and screened for eligibility. Then, participants will perform a logical memory test, immediate recall test, and 25 minute recall. Participants will also perform a verbal fluency test. KVLT-R and BVMT-R and Rey Complex Figure test (RCFT).

Visit 2

Healthy subjects will perform the 1 week retrieval for the logical memory task, be given instructions for the scan test, and undergo the first set of MRI and fMRI scans.

Visit 3

Healthy subjects will complete the second set of MRI and fMRI scans.

Visit 4

Subjects will perform a memory recall task from the fMRI scan on visit 3 and a story segmentation task based on the fMRI scan on visit 2..

Data Analysis and Data Monitoring

Analysis Plan:

Primary: Between treatment differences in PSYRATS Delusions Subscale

Mean effects in week 12. The mean effect of DCS + CBT compared to Placebo + CBT on delusions will be tested using a linear mixed model repeated measures (MMRM) analysis of modified PSYRATS with fixed terms for study visit, DCS/Placebo treatment group and visit by treatment interaction. The model will include random subject effects. Baseline PSYRATS will be included in the model together with a baseline by treatment interaction term. The MMRM will assume a means model, an unstructured covariance matrix and parameter estimation will be based on restricted maximum likelihood. Because of the potential for failure of model convergence due to the requirement of a large number of interaction terms, only a few other covariates will be considered. These may include baseline SANS total score and demographic variables including age and gender, which may be predictive of outcome. To test treatment difference in change from baseline in PSYRATS, we will use a-pairwise contrast on the terms for DCS treatment by visit interaction. To examine differential treatment effects at each CBT week if there is significant interaction, we will perform tests of simple main effects. A significantly larger 12-week decline in mean PSYRATS total score for subjects receiving DSC supports the

Study #:S12-02991

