c. Characterizing the population of responders. An alternative approach to characterizing onset when there is a substantial fraction of the population who will never respond is to use a "cure model" (48, 49). The approach was recommended by consensus, in a specially organized conference to develop an approach to measuring onset in GAD (49). The recommended model assumes that $H(t) = (1-p) + pS(t)$ where $H(t)$ is the survival distribution for the full population, $S(t)$ is the conditional survival probability of onset, given that onset will occur and p is the probability that onset will occur e.g., that the subject is a responder. In the parametric approach, the probability of response, p , will be modeled with a logistic and $S(t)$ will be modeled with a Weibull. The equality of the values of p for placebo and DSC will be compared using a likelihood ratio test. There are many tests of equal conditional survival distribution summarized in Laska (49). In the statistical models for p and for $S(t)$, baseline variables can be included as covariates. Those that are statistically significant and that have high influence will be used to identify the population of patients most likely to be responders in subsequent trials. Nonparametric estimates of the probability of response at the end of the treatment period and of the conditional survival distribution of onset for those achieving onset can also be obtained to confirm the results of the parametric model. The Laska-Meisner test will be used to test equal probability of achieving onset (50). (Remove the current 50 and change reference 51 to 50)

Tertiary: Identify mediators of delusional response to DCS

a. Memory Consolidation Hypothesis. The primary MMRM model described above will be used to test the predictive value of 7-day delayed thematic recall on the Logical Memory Test after the first dose of DCS. The baseline covariates in MMRM analysis of modified PSYRATS, will be augmented by the recall value. If statistically significant, a test of the hypothesis that the coefficient of the recall term in the model is not zero will demonstrate the predictive value of the measure. The magnitude of the coefficient is a measure of the degree to which the variable effects the PSYRATS score at week 12. The data for this analysis is restricted to those subjects randomized to DCS.

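### Hypothesis 3a is about change in recall, but the analysis enters only the post-dose recall value; the week-12 target of the coefficient also needs a visit term

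*Combined protocol and SAP*

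**What the plan says.** **The hypothesis.** Purpose of the Study, Tertiary 3a: "Change in 7-day thematic recall on the Logical Memory Test after the first dose of DCS will predict improvement" on the PSYRATS Delusions Subscale at 12 weeks.

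**The analysis.** Analysis Plan, Tertiary a, will use the primary MMRM to "test the predictive value of 7-day delayed thematic recall on the Logical Memory Test after the first dose of DCS". It continues: "The baseline covariates in MMRM analysis of modified PSYRATS, will be augmented by the recall value". The decision rule is that "a test of the hypothesis that the coefficient of the recall term in the model is not zero will demonstrate the predictive value". The interpretation is: "The magnitude of the coefficient is a measure of the degree to which the variable effects the PSYRATS score at week 12". The analysis set is one arm: "The data for this analysis is restricted to those subjects randomized to DCS".

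**The model it borrows.** Analysis Plan, Primary, describes an MMRM "with fixed terms for study visit, DCS/Placebo treatment group and visit by treatment interaction", plus baseline PSYRATS and its interaction with treatment. No covariate-by-visit term is named, and the visits in the model are not listed.

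**The data available.** Assessment of memory consolidation has Story A given one week before baseline, with its 7-day recall tested at baseline. Story B is given at week 3 after study drug and is "tested for delayed thematic recall immediately prior to administration of study drug the following week". A pre-drug and a post-drug 7-day recall therefore exist for each subject.

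**The concern.** There are two gaps between the hypothesis and its test, and they differ in strength.

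The first is explicit. The hypothesis names a change; the analysis names a value. A subject with good memory throughout and a subject whose recall improved after DCS can have the same Story B score. With no Story A term, and no placebo slope for comparison, the coefficient cannot tell them apart. This does not look like shorthand: the neighbouring analysis 3b asks for a change score, and the synergy analysis 3c sets the delayed recall measure beside the change in alternative beliefs.

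The second is inferred. Recall is added to the baseline covariates, one coefficient is tested, and no interaction with visit is mentioned. In the DCS-only subset the treatment terms drop out, which leaves one recall slope shared by every modelled visit. The plan reads that slope as the effect at week 12. The two agree only if recall has the same association with PSYRATS at every visit. That is hard to expect at weeks 2 and 3, because Story B recall is not measured until week 4.

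At stake is what the mechanistic result means. A null could reflect a diluted predictor or a diluted time frame, and a positive could partly reflect memory level.

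**Working it through.** The documents give no sample size, power or effect size for 3a, so there is no planned figure to reproduce. The check compares the hypothesis with the model.

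**1. Value versus change.** Assume equal variances for Story A and Story B recall and a correlation r between them (not given in the documents). Then corr(B, B − A) = √((1 − r)/2).

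| r (assumed) | corr(B, B − A) | shared variance |
|---|---|---|
| 0.4 | 0.55 | 30% |
| 0.5 | 0.50 | 25% |
| 0.6 | 0.45 | 20% |
| 0.7 | 0.39 | 15% |

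Conversely, if only Story A level were related to PSYRATS, the slope on Story B would be r times the slope on Story A, so 0.4 to 0.7 of it. Adjustment for baseline PSYRATS would absorb part of this.

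**2. Averaged slope versus week-12 slope.** For a covariate that is constant over time, the generalised least squares main effect is a weighted mean of the visit-specific slopes, with weights S⁻¹1 / (1′S⁻¹1), where S is the covariance matrix over visits. The Assessments section puts the delusions subscale at weeks 4, 8 and 12 (clinical battery) and at weeks 2, 3, 6 and 10 (extra ratings). Assumed S: compound symmetry with correlation 0.7, or autoregressive with 0.8 per two weeks. Three slope profiles are assumed, each scaled to 1 at week 12.

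Worked example, compound symmetry (equal weights), linear rise from week 3 to week 12, so slope (week − 3)/9:
- Seven visits: (0 + 0 + 1/9 + 3/9 + 5/9 + 7/9 + 1)/7 = (25/9)/7 = 0.40.
- Weeks 4, 8, 12: (1/9 + 5/9 + 1)/3 = 0.56.

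Under the autoregressive form the seven weights are 0.34, 0.04, 0.05, 0.07, 0.07, 0.07 and 0.36; for weeks 4, 8 and 12 they are 0.42, 0.15 and 0.42. Ratios of averaged to week-12 slope across both covariance forms:

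| Assumed time course | Seven visits | Weeks 4, 8, 12 | Weeks 6, 8, 10, 12 |
|---|---|---|---|
| Linear, week 3 to 12 | 0.40–0.48 | 0.56 | 0.67 |
| Plateau by week 8 | 0.54–0.55 | 0.66–0.73 | 0.83–0.90 |
| Step after week 3 | 0.63–0.71 | 1.00 | 1.00 |

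The last column shows that keeping only visits after week 4 shrinks the gap but is not equivalent to a week-12 contrast.

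**3. Timing of the week-3 rating.** CBT/DCS Protocol places the first DCS dose one hour before session 3. Assessments says ratings come before each week's DCS/CBT session. Together these put the week-3 rating before the first dose. Estimation of statistical power, however, describes week 3 as the first clinical assessment after study drug. The passages disagree and must be reconciled.

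**The case against.** The strongest reply is that the visit argument rests on silence. The plan never says main effect and never lists the MMRM visits. The extra ratings at weeks 2, 3, 6 and 10 are there to describe time course, so a primary model on weeks 4, 8 and 12 fits the text too, although the reference to effects at each CBT week allows more visits. With three visits and a step profile nothing is lost. The protocol also anticipates a plateau, which makes the linear profile behind the lowest ratios less natural. If the week-3 rating is post-dose and the step begins there, the seven-visit ratio is 0.66 to 0.86. The plan clearly means to target week 12, so the missing visit term may be under-specification. All of this stands, and it is why the visit part is a request to specify and improve.

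A cost objection also stands. About 30 subjects (half of 60 evaluable) with seven visits and an unstructured matrix means 7 × 8/2 = 28 covariance parameters. A recall-by-visit term adds six more coefficients, and the plan itself warns about convergence.

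None of this answers the predictor mismatch. Both wordings are in the document, and Story A recall is already collected.

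A reader might infer that the coefficient measures neither thing, that Story B recall is mostly trait memory, or that a positive result would give no support to 3a. The documents do not carry that far. They give no Story A to Story B correlation, and on the assumed range the raw value is a confounded and attenuated proxy, not an uninformative one.

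**Conclusion.** Wrong as written for the predictor: the plan tests recall level in the DCS arm where the hypothesis concerns change in recall. Under the assumed correlations of 0.4 to 0.7 with equal variances, the entered variable correlates 0.55 to 0.39 with the hypothesised one. The mismatch itself needs no assumption.

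A cheap improvement for the week-12 term: on the most natural reading the coefficient is an average over visits, about 0.40 to 0.71 of the week-12 slope with seven visits and 0.56 to 1.00 with weeks 4, 8 and 12. These ranges depend on the unstated visit set, the assumed covariance and the assumed time course. The ratio is 1 whenever the slope is the same at every modelled visit.

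The consequence is confined to tertiary 3a, the recall term in 3c, and, for the week-12 term only, 3b, which already uses a change score. The primary result is unaffected.

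**What to change.** 1. In 3a, and for the recall term in 3c, enter Story B recall together with Story A recall, or enter the A-to-B change. The first is preferable. With Story A in the model the Story B coefficient equals the coefficient of the change, since b₁B + b₂A = b₁(B − A) + (b₁ + b₂)A. The change alone is correlated with Story A at −√((1 − r)/2).
2. List the visits in the model.
3. Add covariate-by-visit in 3a, 3b and 3c and test the week-12 coefficient. If the unstructured model does not converge with about 30 subjects, regress week-12 PSYRATS on baseline PSYRATS and the predictor(s); state this fallback in advance.
4. Reconcile CBT/DCS Protocol, Assessments and Estimation of statistical power on whether the week-3 rating precedes the first dose.

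Cost: analysis-plan wording and no new data. Story A takes one degree of freedom. The visit interaction takes two more per covariate with three visits or six with seven, which is not trivial in a one-arm analysis and is the reason for the fallback. The regression fallback uses only subjects with a week-12 rating, so it gives up the MMRM's use of partial follow-up.

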effectiveness of DCS. The probability of a type one error, the size of the test, will be controlled at 0.05, and all tests will be two-tailed. Overall alpha will be maintained at 0.05 for analyses of primary parameters. No adjustments will be made for multiplicity among secondary parameters analyzed. *Missing data*: The analysis will utilize the intention-to-treat principle. All randomized subjects, both completers and non-completers, will be included in the analysis without imputation. Estimates will be unbiased if follow-up data that are missing are "missing at random" conditional on the observed data and model assumptions.

Secondary: Characterizing onset and duration of effectiveness of DCS

a and b. Testing equality of the distributions of onset and duration. Onset is defined as the first week at which the criterion for response is met that lasts at least to the final week of the treatment period. Kaplan-Meier estimates of the survival distributions of time to onset of response will be obtained and the survival distributions will be compared using the log-rank test. The survival distribution, $H(t)$, is the probability that onset will occur after time t . Duration is defined as the number of weeks from onset to offset. Offset for a responder is the first week at which the criterion for response is no longer met. The treatment specific survival distributions of duration will similarly be compared using the log-rank test. The null hypothesis for the second primary outcome measure is that there is no difference between the two treatment groups in the proportion of subjects who are responders (defined as a 20% or greater reduction in PSYRATS Delusions Subscale total score) beginning in week two to the end of the treatment phase. The statistical analysis will be based on a repeated measures logistic regression model. The independent terms in the model will include the same variables and covariates used in the MMRM analysis. By the definition of responder, there cannot be any missing data.

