b. Cognitive Flexibility Hypothesis. Just as for the memory consolidation hypothesis, the primary MMRM model described above will be used to test the predictive value of change in the number of alternative beliefs generated during the first and second administrations of the Alternative Beliefs Exercise in the DCS group on the week 12 PSYRATS score. The baseline covariates in MMRM analysis of modified PSYRATS, will be augmented by the change score.

c. Synergy Hypothesis. The primary MMRM model described above will be used to test whether

Study #:S12-02991

positive outcomes on both the 7-day delayed thematic recall measure and the change in the number of alternative beliefs measure produces better outcomes on the week 12 PSYRATS score than would be expected by additivity. The analysis will also investigate whether outcomes needs to be positive in both variables for the DCS treatment to be effective. In this analysis, the model will contain both covariates and an interaction term. If the interaction term is statistically significant, the sign of the estimated coefficient will indicate synergy/antagonism and the magnitude of the coefficient together with the magnitude of the coefficients of the recall and change measure quantifies the joint effect on the PSYRATS week 12 score.

Data Storage and Confidentiality:

Data Management and Quality Assurance: The Principal Investigator has extensive experience in conducting clinical research studies. Based upon this experience, a comprehensive data management methodology combined with strong planning, control, coordination and quality assurance functions will be implemented. The primary objectives of the data management methodology are to insure the completeness, accuracy and overall integrity of the study data.

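### Mediator tests a and b put one predictor coefficient into an unstructured REML model fitted to about 30 DCS subjects; with no small-sample standard error named, the literal nominal 5% test rejects about 10–15% of the time

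*Combined protocol and SAP*

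**What the plan says.** All references are to the combined protocol and SAP.

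- **Model.** Analysis Plan, Primary: "The MMRM will assume a means model, an unstructured covariance matrix and parameter estimation will be based on restricted maximum likelihood". No standard error or degrees-of-freedom method is named there or elsewhere.
- **Test a (memory consolidation).** Analysis Plan, Tertiary: "The primary MMRM model described above will be used to test the predictive value of 7-day delayed thematic recall". Recall enters as one more baseline covariate: "The baseline covariates in MMRM analysis of modified PSYRATS, will be augmented by the recall value". A single coefficient is tested ("a test of the hypothesis that the coefficient of the recall term in the model is not zero will demonstrate the predictive value"), and no recall-by-visit term is mentioned. "The data for this analysis is restricted to those subjects randomized to DCS".
- **Test b (cognitive flexibility).** It is set up in the same way, for the DCS group: "the primary MMRM model described above will be used to test the predictive value of change in the number of alternative beliefs".
- **Test c (synergy).** It uses the same model with both predictors and their product. No restriction to the DCS arm is stated.
- **Target.** Both tertiary mediator hypotheses in the Specific Aims concern improvement at 12 weeks. Test a interprets its coefficient as an effect on the week-12 score, and tests b and c name the week-12 score as the outcome.
- **Error rate.** Analysis Plan, Primary: "The probability of a type one error, the size of the test, will be controlled at 0.05, and all tests will be two-tailed". The next sentence keeps overall alpha at 0.05 for the primary parameters only.

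**The concern.** A slope common to all visits is estimated by weighting the visits with the inverse of the estimated covariance matrix. The usual model-based standard error treats that matrix as known. With seven visits and about 30 subjects it is poorly known, so the estimate varies more than its standard error says, and the test rejects too often.

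The plan reads a significant coefficient as demonstrating predictive value, and finding mediators is a stated aim. An uncorrected analysis could therefore report memory consolidation or cognitive flexibility as a predictor of response by chance two to three times as often as the nominal level suggests. Separately, a slope averaged over visits does not answer a question about week 12.

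**Working it through.** **Inputs**
- DCS arm: 60 evaluable at 1:1 gives 30 (Estimation of statistical power); 64 randomized gives 32 (Number of Subjects). As a check, 30 per arm at effect size 0.8 gives power of 0.86–0.87, which agrees with the plan's figure of more than 85%.
- PSYRATS Delusions ratings up to week 12: weeks 2, 3, 4, 6, 8, 10 and 12 (Assessments), so 7 visits. Weeks 4–12 alone give 5.
- Covariance parameters: 7 × 8 / 2 = 28 for 7 visits; 5 × 6 / 2 = 15 for 5.
- Nominal level: 0.05, two-sided. The plan asserts this figure and does not derive it.
- Dropout: no rate is given. Complete data and an assumed 25% monotone dropout were both examined.

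**Approximate size of the standard error problem (complete data)**

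Let ν be the error degrees of freedom: 30 minus 3 (intercept, baseline, recall) = 27. Let k be the number of visits. For a pooled slope,

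reported SE / true SD ≈ √{ [(ν − k + 1)/ν] / [(ν − 1)/(ν − k)] }.

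- k = 7: √[(21/27)/(26/20)] = √(0.778/1.300) = 0.77, so the SE is about 23% too small.
- k = 5: √[(23/27)/(26/22)] = √(0.852/1.182) = 0.85, about 15% too small.

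Multiplying the critical value by this ratio and referring it to t with 27 df approximates the true rejection rate:
- k = 7: 2.052 × 0.7735 = 1.587, giving 12.4%; with the normal cut-off, 1.96 × 0.7735 = 1.516, giving 14.1%.
- k = 5: 2.052 × 0.849 = 1.742, giving 9.3%; with the normal cut-off, 1.96 × 0.849 = 1.664, giving 10.8%.

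**Simulation of the literal model under the null** (REML, unstructured; visit means plus one baseline slope and one recall slope; 4,000 trials with complete data, 1,200 with dropout)

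| Setting | t, between-subject df | Normal reference |
|---|---|---|
| n = 30, 5 visits | 9.7% | 11.1% |
| n = 30, 7 visits | 13.2% | 14.8% |
| n = 32, 7 visits | 12.1% | 13.5% |
| n = 30, 7 visits, plus SANS, age, gender | 14.0% | 15.8% |
| n = 30, 5 visits, 25% dropout | 13.1% | 14.1% |
| n = 30, 7 visits, 25% dropout | 14.4% | 15.6% |

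Separate simulations with complete data gave 8.9–10.6% for 5 visits and 11–15% for 7. At 7 visits the simulated SE was 21–26% too small. Satterthwaite degrees of freedom gave the same rejection rates as the between-subject t in the complete-data runs, because the fault lies in the SE and not in the reference distribution.

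**Alternatives, n = 30**
- Pooled slope with Kenward-Roger: 6.3% (5 visits), 7.4% (7 visits), 8.3% (7 visits with the three extra covariates), 6.0% (7 visits, 25% dropout).
- Recall crossed with visit and tested at week 12, 7 visits: 5.6% (t) or 7.1% (normal); with 25% dropout, 7.0% or 7.9%.
- Ordinary regression of week-12 PSYRATS on baseline and predictor: about 4–5%.

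**Other tests**
- Test c in all 60 subjects with a treatment term, 7 visits: 7.1% (t) or 7.8% (normal).
- Primary week-12 treatment contrast in 60 subjects: about 3–5%.

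**The case against.** The strongest reply is that the plan is silent on the standard error and does not rule out a correction. This is true: with Kenward-Roger the literal model comes to about 6–8%. But the choice moves the rejection rate by several points and is not fixed in advance, and common software defaults or a change of degrees of freedom alone would leave the inflation in place.

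The second reply is that the text points to week 12, so recall may be meant to interact with visit. The hypotheses and all three tertiary tests do name week 12, and that version would give about 6–8%. However, the plan describes a single added covariate and a single coefficient, with no interaction. The two descriptions cannot both hold, so the text needs repair under either reading.

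Three stronger readings are tempting but not supported:
- *Error rates near 19%.* These require weeks 24 and 36 in the model. The primary section is headed as a week-12 analysis, and the plan does not say which visits enter the mediator models. Ratings precede each session and active drug starts at session 3, so even weeks 2 and 3 could reasonably be left out.
- *All three tests are confined to the DCS arm.* This is explicit for test a and follows from the wording of test b. It is not stated for test c.
- *The plan breaks a 5% promise.* The 0.05 statement stands in the primary section, and overall alpha is maintained only for primary parameters. These tests are tertiary, in a trial that calls itself proof-of-concept.

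**Conclusion.** The point stands for tests a and b as literally written. With about 30–32 DCS subjects, one slope common to all visits and a model-based standard error, a nominal 5% test rejects about 10% of the time with five visits and about 11–15% with seven when data are complete. An assumed 25% dropout raises the five-visit figure to 13–14% and puts the seven-visit figure at 14–16%. These figures assume normal errors and no small-sample correction. They fall to about 6–8% if Kenward-Roger is used or if the predictor is tested at week 12 through a visit interaction.

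For test c, the rate is about 7–8% if all 60 subjects are analysed. The pooled slope also differs from the stated week-12 target, whatever its error rate. A reader might infer that the main efficacy result is unsafe too; it is not, since the primary week-12 contrast keeps its size. This should be corrected, but it bears on the mediator claims only.

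**What to change.** In the Tertiary part of the Analysis Plan:

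1. Cross the predictor with visit in tests a to c, and likewise the product term in test c. Test the week-12 coefficient.
2. Use Kenward-Roger standard errors and degrees of freedom for these repeated-measures tests.
3. State which visits enter the models, and whether test c uses the DCS arm or all randomized subjects.
4. Report, as a sensitivity analysis, an ordinary regression of week-12 PSYRATS Delusions on baseline PSYRATS and the predictor or predictors, with t-based inference. It should not decide the test, because it drops subjects without a week-12 rating, whereas the plan includes non-completers.

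The cost is a few sentences and one software option, with no new data or visits. P-values will be somewhat larger, and the model gains a few parameters: six more slopes per predictor with seven visits (7 − 1). Items 1 and 2 were each checked separately but not in combination, so a short simulation at the planned arm size would be a sensible confirmation.
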